11.6. Pregnancies

Listings of subjects with data from the “Childbearing Potential” and “Pregnancy Test” eCRF pages will be provided.

11.7. Karnofsky or Lansky Performance Status Score

Performance status will be measured using either the Karnofsky performance status (Karnofsky, 1949) or Lansky performance status (Lansky 1987) score (Karnofsky performance status score for subjects ≥ 16 years of age or Lansky performance status score for subjects < 16 years of age) at screening, on Day 1 of each cycle, Treatment Discontinuation Visit, and at the 28-Day Post Treatment Safety Follow-up visit, refer to [Appendix A2 Section 58](#). For performance status scores, shift from baseline to worst value and best score during the treatment period will be displayed for the whole treatment period and by cycle in a summary table for the Safety

Population. Summary tables will show the data presented by tumor type/disease indication, and in aggregate.

Performance status scores will also be presented in a listing for the ITT Population.

CELGENE PROPRIETARY INFORMATION

12. PRIMARY AND END OF STUDY FINAL ANALYSES

All tables, listings and figures detailed in this SAP will be provided for the primary final analysis that will be conducted when all on treatment subjects will have completed their 28-Day Post Treatment Safety Follow-up visit, 28 days post last dose of pomalidomide.

For the end of study final analysis, all outputs will be rerun once all subjects will have discontinued the follow-up period (up to 5 years after the last subject enrollment date).

REFERENCES

Brookmeyer R and Crowley J. A confidence interval for the median survival time. *Biometrics* 1982;38:29-41.

Kaplan E L and Meier P. Nonparametric estimation from incomplete observations. *Journal of the American Statistical Association* 1958;53(282):457-481.

APPENDIX A1 – REPORTING CONVENTIONS

The summary tables, listings, and any supportive SAS output will include the explanatory “headers” that indicate, at a minimum:

- protocol number;
- database cutoff date, displayed as DDMONYYYY;
- company name (Celgene);
- page number (Page x of x).

The summary tables, listings, and any supportive SAS output will include the explanatory “footers” that indicate, at a minimum:

- program source (ie, SAS program name, including the path, run date);
- data extraction date, displayed as DDMONYYYY;
- data source (ie, list of datasets used for the display);
- run time (ie, when the program was run), displayed as DDMONYYYY:HH:MM.

The purpose of the data extraction date is to link the output to the database, either active or archived, that is write-protected for replication and future reference. The program run date is the output date which will appear on each output page and will indicate the date the output was generated by the analysis program. Individual source listings will display all the relative values supporting corresponding table(s) and figure(s).

In addition, the following reporting conventions will be implemented:

- Data from all study sites will be combined for analysis;
- Confidence intervals (CIs) will be presented as 2-sided 95% CIs unless otherwise specified;
- Summary statistics will consist of the number and percentage of subjects in each category for discrete variables, and the sample size (n), mean, median, standard deviation (StaDev), minimum (Min), and maximum (Max) for continuous variables and displayed as follows:

n	xx
Mean	xx.x
StdDev	xx.xx
Median	xx.x
Q1, Q3	xx.x, xx.x
Min, Max	xx, xx

- For analyses where the sample size, n, is 1, the StaDev will be displayed as ‘NA’;
- All mean and median values will be formatted to 1 more decimal place than the measured value. Standard deviation values will be formatted to 2 more decimal places than the measured value;
- P-values will be rounded to 4 decimal places. P-values that round to 0.0000 will be presented as ‘<0.0001’ and p-values that round to 1.000 will be presented as ‘>0.9999’;

- All percentages will be rounded to 1 decimal place. The number and percentage of responses will be presented in the form xx (xx.x), where the percentage is in the parentheses. In the case the numerator is equal to the denominator, the percentage should be presented as (100) instead of (100.0);
- If the numerator is '0' then show '0'. If the denominator is '0', then show 'NA' - apply this logic for descriptive stats;
- All listings will be sorted for presentation in order of tumor type/disease indication, study site, subject number, and date of procedure or event. Subjects who are not enrolled will be listed as a non-enrolled group after enrolled subjects;
- In listings, a day reported in relation to treatment start but which is unknown due to an unknown/partially reported date, will be presented with a hyphen;
- In listings, unknown/missing dates will be reported as 'unknown', while the unknown part of a partial date will be presented as 'UN';
- All tables will be presented by tumor type/disease indication;
- In tables where a parameter/category is displayed over several lines, the statistic will be presented on the top line;
- All analysis and summary tables will have the analysis population sample size for each treatment group in the column heading (ie, number of subjects) where applicable;
- Baseline is defined as the latest value collected on or before the date when the first dose of study treatment is administered. If multiple values are present for the same date, the mean of these values will be used as the baseline, except for laboratory data, where the value with the worst Common Terminology Criteria for Adverse Events (CTCAE) grade will be set as baseline. For subjects who were not treated, the baseline value will be defined as the latest value collected on or prior Day 1 of the Cycle 1 visit, if available;
- The day of first dose of study drug pomalidomide will be defined as Day 1. For subjects who are not treated, the Cycle 1 Day 1 visit will be defined as Day 1;
- For tables and figures displaying results by visit, only scheduled visits will be considered beside clinical laboratory evaluations. Unscheduled visits will appear only in listings and could be considered in some derivations;
- The title of the TLG will be centrally justified with the analysis population used directly beneath the title of the TLG, while the TLG number will be in the line directly above the TLG title. The TLG number will be preceded with the text 'Table:', 'Listing:' or 'Figure:', depending on the nature of the output;
- The TLG number will not include alphabetical values;
- The title of the TLG should not include a reference to a footnote;
- The TLG footnotes should follow the following convention for ordering footnotes:
 - Abbreviations

- Additional footnotes
 - Anchored footnotes, i.e. [a], [b], etc.
 - A line break
 - Program Path
 - Data Source / Data Extraction Date / RunTime;
- Each individual footnote should start on a new line, and end with a full stop;
 - The use of the text ‘Note:’, is not permitted in a footnote;
 - Abbreviations used in the main body of the TLG or footnote which are which are not explained as part of a footnote will be explained in the first line of footnote(s), i.e. the abbreviations footnote;
 - Throughout the TLGs, instead of m^2 or $m2$, m^2 must be used;
 - Instead of \leq and \geq , \leq and \geq must be used with a space preceding and a space succeeding the symbol;
 - References linked to footnotes must be anchored using character instead of numeric values, ie, use [a], not [1];
 - Footnotes that explain abbreviations or categories will use ‘=’ without a space on either side, and be separated with a comma and not a semicolon;
 - When a footnote refers to something in the table, such as Race, there is no need to say “Race: “, in the footnote itself;
 - In the main body of the TLG or the TLG footnote(s), if text is used to demonstrate a range, then use ‘to’, and not ‘-’, with a space on either side of the word ‘to’.

APPENDIX A2 – CONVENTIONS RELATED TO DATES

Following are the general conventions for various computations and imputations for references. Users may need to consult with study team for specific study practices or regulatory guidelines.

1. Handling of Dates

Dates will be stored as numeric variables in the SAS analysis files and reported in DDMMYY format (ie, the Date9. date format in SAS). Dates in the clinical database are classified into the categories of procedure dates, log dates, milestone dates, outcome dates, and special dates.

- **Procedure Dates** are the dates on which given protocol-specified procedure are performed. They include the dates of laboratory testing, physical examinations, tumor scans, etc. They should be present whenever data for a protocol-specified procedure are present and should only be missing when a procedure are marked as NOT DONE in the database. Procedure dates will not be imputed.
- **Log Dates** are dates recorded in eCRF data logs. Specifically, they are the start and end dates for adverse events and concomitant medications/procedures. They should not be missing unless an event or medication is marked as *ongoing* in the database. Otherwise, incomplete log dates will be imputed according to the rules in section 4.1 and section 4.2 of this Appendix. However, in listings, log dates will be shown as recorded without imputation.
- **Milestone Dates** are dates of protocol milestones such as randomization, study drug start date, study drug termination date, study closure date, etc. They should not be missing if the milestone occurs for a subject. They will not be imputed.
- **Outcome Dates** are dates corresponding to study endpoints such as survival, progression, etc. In most cases they are derived either from a milestone (eg, the survival date is derived from the death date), or a procedure date (eg, the progression date is derived from the date of the tumor scan that was used to determine progression). They may be subject to endpoint-specific censoring rules if the outcome did not occur, but are not otherwise subject to imputation.
- **Special Dates** cannot be classified in any of the above categories and they include the date of birth. They may be subject to variable-specific censoring and imputation rules.

Dates recorded in comment fields will not be imputed or reported in any specific format.

2. Calculations Using Dates

Calculations using dates (eg, subject's age or relative day after the first dose of study drug) will adhere to the following conventions:

- Study days after the start day of study drug will be calculated as the difference between the date of interest and the first date of dosing of study drug (eg, pomalidomide) plus 1 day. The generalized calculation algorithm for relative day is the following:
 - If TARGET DATE \geq DSTART then STUDY DAY = (TARGET DATE – DSTART) + 1;
 - Else use STUDY DAY = TARGET DATE – DSTART.

Note that Study Day 1 is the first day of treatment of study drug. Negative study days are reflective of observations obtained during the baseline/screening period. Note: Partial dates for the first study drug are not imputed in general. All effort should be made to avoid incomplete study drug start dates. Some analyses may exclude subjects without study drug start date. The SAP may be amended on a case-by-case basis, including guideline and suggestion such as imputing Day 1 by consent date of treated subject.

- Age (expressed in days) is calculated: AGE = CONSENT – DATE of BIRTH + 1. In practice, age will be transformed to years by dividing the difference by 365.25 days, then truncating.
 - Preference is for using calculated age from clinical database. When not available, calculated age from eCRF or IVRS may be used.
 - Partial birth date: impute missing day as 15th of the month; impute missing month as July; set missing age for missing year. Should the imputed age succeed an earlier assessment date collected for that subject, the imputed month will be set to the month preceding the assessment date.
- Intervals that are presented in weeks will be transformed from days to weeks by using (without truncation) the following conversion formula:

$$\text{WEEKS} = \text{DAYS} / 7.$$

- Intervals that are presented in months will be transformed from days to months by using (without truncation) the following conversion formula:

$$\text{MONTHS} = \text{DAYS} / 30.4375.$$

3. Calculations of Cycles

Treatment will commence on Day 1 and planned cycle lengths are 28 days. Day 1 of treatment is defined as the first day of actual study drug administration. Day 1 of a cycle is defined as day 1 of study drug for the given cycle as recorded on the eCRF.

Cycle end dates are defined as the day before Day 1 of the following cycle, or if on the last cycle then the last day is the last treatment administration date plus 28 days, i.e. the treatment end date plus 28 days. The treatment end date, and the end date of the last cycle, will be calculated as follows:

- For subjects who discontinue prior to the clinical cutoff date, treatment end date is the date of treatment discontinuation from the treatment disposition page in the eCRF;
- For subjects who are still on treatment at the time of study closure or clinical cutoff, the last date of planned cycle (27 days after first dose of the last cycle) will be used as the treatment end date.

The cycle number for each date of interest, eg, AE start date, will be calculated based on the cycle window set by their start and end dates.

The following rules will be implemented for cycle calculations for TEAEs:

- TEAEs present on or after Day 1 Cycle i but before Day 1 of the subsequent cycle belong to Cycle i (where i stands for cycle number);
- All TEAEs that occur between Day 1 of the last cycle and 28 days after last dose administration date will be included only in the last cycle.

4. Guideline of Missing Date Imputation

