9.7. Safety Analysis

Toxicity Assessment

Toxicity, including SPMs, will be monitored in real time during the course of the study. Descriptive statistics will be used to summarize the proportion of subjects experiencing any Grade 3 or higher non-hematologic toxicities and infections.

Adverse Events

Adverse Events will be coded according to the Medical Dictionary for Regulatory Activities (MedDRA) (latest version). This study will utilize the NCI CTCAE (version 4.03) for toxicity grading and performance reporting. All AE data shall be presented by disease stratum and in aggregate, based on the Safety Population, ie, all subjects receiving at least one dose of pomalidomide.

Treatment-emergent adverse events are defined as any AE occurring or worsening on or after the first dose of the study medication until the 28-day post-treatment Safety Follow-up Visit. All TEAEs, AEs leading to study medication discontinuation, AEs leading to dose reduction/interruption, AEs related to the study treatment, SAEs, and AEs leading to death will be summarized by cycle and 28-day follow-up period after permanent treatment discontinuation as well as by subject (worse recorded grade) per event type (organ class and preferred term) and grade. A summary of AEs with NCI CTCAE (version 4.03) Grade 3 or higher, as well as the most frequent preferred terms, will also be provided by grade and term.

Cross tabulations will be provided to summarize frequencies of abnormalities.

By-subject listings will be provided for all relevant safety data. Graphical displays and figures will be provided where useful to assist in the interpretation of results.

Deaths

Deaths during the Treatment Period (defined as the time between enrollment until the 28-day post-treatment Safety Follow-up Visit) and during the Follow-up Period shall be summarized by frequency of occurrence and corresponding percentage by cause of death per study period (during treatment or follow-up) as well as overall. All death data shall be presented by disease stratum and in aggregate.

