11.1. Adverse Events

Adverse Events will be coded according to MedDRA dictionary version 21.0 or higher. The severity of AEs will be graded according to the National Cancer Institute (NCI) Common Terminology Criteria for Adverse Events (CTCAE), version 4.03, May 2009, or later.

All AEs will be recorded by the Investigator from the time the subject signs the ICF/IAF until 28 days after the last dose of pomalidomide and those SAEs made known to the Investigator at any time thereafter that are suspected of being related to pomalidomide.

In the occurrence of partial dates, refer to [Appendix A2 Section 4.1](#) where date the imputation guideline is located.

Treatment-emergent adverse events (TEAEs) are defined as any AE occurring or worsening on or after the first dose of pomalidomide and within 28 days after the last pomalidomide administration date. Adverse events leading to death that occur after 28 days post the last pomalidomide administration but are the end result of an ongoing AE that started during the treatment period, or started prior to first dose of pomalidomide but worsened in severity during the treatment period, are considered treatment-emergent. All TEAEs, AEs leading to IP discontinuation, AEs leading to dose reduction/interruption, AEs related to pomalidomide, and SAEs and AEs leading to death will be summarized by cycle up to a 28-day period after last cycle (refer to [Appendix A2 Section 3](#)), as well as by subject worst recorded grade per event type, SOC, PT and grade. A summary of AEs with NCI CTCAE version 4.03 Grade 3 or higher, as well as the most frequent PTs, will also be provided by grade and PT. If a subject experiences the same AE more than once with different severity grade, then the event with the highest grade will be tabulated in “by grade” tables. If a subject experiences multiple AEs under the same PT/SOC, then the subject will be counted only once for that PT/SOC. In addition, AEs with a missing intensity will be presented in the summary table as an intensity category of “Missing”. Pretreatment AEs will be summarized by PT and SOC.

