11.1.2. TEAEs by System Organ Class and Preferred Term

The incidence of TEAEs will be summarized by MedDRA SOC and PT. The intensity of AEs will be graded 1 to 5 according to the NCI CTCAE.

Tables summarizing the incidence of TEAEs will be generated for each of the following, although not limited to,:

- All TEAEs;
- TEAEs by severity;
- TEAEs with severity of grade 3 and/or 4;
- TEAEs with severity of grade 5 (leading to death);
- TEAEs related to pomalidomide;
- TEAEs related to pomalidomide by severity;
- TEAEs related to pomalidomide with severity of grade 3 and/or 4;
- Serious TEAEs;
- Serious TEAEs related to pomalidomide;
- TEAEs leading to pomalidomide dose discontinuation;
- TEAEs leading to pomalidomide dose reduction;
- TEAEs leading to pomalidomide dose interruption;
- TEAEs by cycle onset.

System organ classes are sorted by descending order of frequency of SOC, and by descending order of frequency of PT within SOC, according to the overall column.

Treatment emergent adverse events, treatment-related TEAEs, TEAEs of Grade 3 or 4, and treatment-related TEAEs of Grade 3 or 4 will also be analyzed within the following age subgroups:

- Age category (≥ 1 years to < 6 years, ≥ 6 years to < 12 years, and ≥ 12 years).

Listing of AE, SAE, SAE of special interest and AE leading to treatment discontinuation will be provided in separated displays, showing the day in relation to the first dose of pomalidomide that the AE began/ended.

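### The SAP counts TEAEs from the 28 days after the last dose in the subject's last cycle, where the protocol reports that period separately; by-cycle percentages are biased upward in cycles where subjects stop

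*SAP*

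**What the plan says.** Protocol 9.7 (Safety Analysis) states that TEAEs and the related AE summaries "will be summarized by cycle and 28-day follow-up period after permanent treatment discontinuation". The follow-up period is a reporting category beside the cycles.

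SAP 11.1 (Adverse Events), the counterpart text, says they "will be summarized by cycle up to a 28-day period after last cycle" and refers to Appendix A2 Section 3. That section contains:

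- the end of the last cycle: "if on the last cycle then the last day is the last treatment administration date plus 28 days";
- the rule for TEAEs: "All TEAEs that occur between Day 1 of the last cycle and 28 days after last dose administration date will be included only in the" final cycle;
- for any other cycle, a window from its Day 1 to the day before the next Day 1, with a planned length of 28 days.

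The affected output is planned: SAP 11.1.2 lists a table of "TEAEs by cycle onset", and SAP 11.1 applies the by-cycle split to the main AE categories. SAP 11.1.1 reports AEs as number and percentage of subjects, and no exposure adjustment is stated. The SAP gives no reason for dropping the separate period.

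SAP 9.1 closes a completed last cycle differently. For treatment duration, a last cycle with 21 days of dosing ends 7 days after the last dose.

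**The concern.** A percentage of subjects with an event depends on how long each subject is watched. Under the SAP rule, subjects who stop in a cycle are watched longer in that cycle than those who continue, and the added time is off drug. The by-cycle percentage then partly reflects how many subjects stopped there. Strata that stop at different cycles would show different time patterns even with the same underlying event rate. A reader of the table could take events from the month after stopping as on-treatment events of that cycle. Safety is a secondary objective here, and the by-cycle tables are where onset over time is shown.

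**Working it through.** The documents state no by-cycle AE rate, so there is no figure of the plan's to reproduce. The check has two parts: the window length, which follows from the rules, and an illustration of its effect, which needs assumptions.

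**Window length.** Inputs: dosing on Days 1 to 21 of a 28-day cycle (Protocol 6.2); the last-cycle TEAE window runs from its Day 1 to last dose + 28 days (SAP A2 Section 3). With the last dose on cycle day d, the window is d + 28 days.

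| Last dose on cycle day | Window (days) | Ratio to 28 | Share after last dose |
|---|---|---|---|
| 1 | 29 | 1.04 | 28/29 = 97% |
| 7 | 35 | 1.25 | 28/35 = 80% |
| 14 | 42 | 1.50 | 28/42 = 67% |
| 21 | 49 | 1.75 | 28/49 = 57% |

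The window always exceeds 28 days unless death or loss to follow-up cuts it short. Measured against a 28-day cycle, a subject's last-cycle count can therefore only stay the same or rise.

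**Effect on the percentage.** Assumptions: constant onset hazard; p = incidence per 28 days; f = share of the cycle's subjects for whom it is the last. The cycle then reads

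(1 − f) × p + f × [1 − (1 − p)^((d + 28)/28)].

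For p = 20% and d = 21, the last-cycle term is 1 − 0.8^1.75 = 1 − 0.677 = 32.3%. With f = 10% the cycle reads 0.9 × 20 + 0.1 × 32.3 = 21.2%; with f = 50%, (20 + 32.3)/2 = 26.2%.

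Reported percentage with the last dose on Day 21:

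| p per 28 days | f = 10% | f = 25% | f = 50% | f = 100% |
|---|---|---|---|---|
| 10% | 10.7 | 11.7 | 13.4 | 16.8 |
| 20% | 21.2 | 23.1 | 26.2 | 32.3 |
| 30% | 31.6 | 34.1 | 38.2 | 46.4 |
| 50% | 52.0 | 55.1 | 60.1 | 70.3 |

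Day 21 is the largest case. With p = 20% and f = 50%, the cycle reads 20.3% for a last dose on Day 1, 22.2% for Day 7, 24.2% for Day 14 and 26.2% for Day 21.

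For an early last dose the excess over 28 days nearly vanishes, but almost the whole window is then post-dose. With p = 30% and f = 100%, a last dose on Day 1 gives 30.9%, against 1.3% if the cycle closed at the last dose.

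**The case against.** Several points on the other side stand.

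- The effect is confined to descriptive by-cycle tables. Overall TEAE incidence, worst-grade tables, the stage decisions and the primary endpoint do not use the cycle window.
- Drug-related AEs are tabulated separately, and the AE listings give onset relative to first dose (SAP 11.1.2), so a careful reader can recover the timing. The related-AE summaries by cycle follow the same window, though, so this helps only in part.
- Assigning post-dose events to the last dosed cycle is a defensible convention in itself. It is not the protocol's, however, and the SAP does not explain the change.
- The 28-day comparator is nominal, because delayed starts lengthen other cycles (Protocol 7.2.1 and 7.2.2). The by-cycle denominator is not stated.
- The size is modest in small strata: 26% against 20% is about one subject in 20.

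A reader might also infer stronger versions that the documents do not support.

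*That the conflicting end dates in A2 Section 3 change the counts.* The section equates last dose + 28 days with treatment end + 28 days, yet for discontinued subjects "treatment end date is the date of treatment discontinuation from the treatment disposition page in the eCRF". With the last dose on Day 21 and discontinuation dated Day 29, the last cycle ends on Day 49 or Day 57; for a subject ongoing at cutoff it could end on Day 56. But the TEAE rule uses the last dose, and SAP 11.1 limits new TEAEs to 28 days after it. No new TEAE can arise on Days 50 to 57, so this is a wording defect with no effect on by-cycle TEAE counts.

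*That disease-related events after progression will pile up in Cycles 2 and 3.* First scheduled scans at Cycle 3 Day 1 (Cycle 4 Day 1 for DIPG) make clustering of stops plausible. But scans are also done when clinically indicated, and neither document gives figures on when or why subjects stop.

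**Conclusion.** The point holds as a departure of the SAP from Protocol 9.7 that biases by-cycle TEAE percentages upward in cycles where subjects stop. The direction and the 29-to-49-day window follow from the SAP's own rules; 1.75 times is the maximum ratio. The size in percentage points is illustrative only. It rests on a constant hazard, on assumed values for incidence and for the share stopping, and on a percentage of subjects as the measure. A person-time rate over the same extended window would not necessarily be inflated. The documents do not support reading this as a threat to the trial's overall safety conclusions or its efficacy decisions. It is worth correcting because a stated rule contradicts the protocol and the correction is nearly free.

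**What to change.** In SAP 11.1 and Appendix A2 Section 3:

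1. Add a separate column for the 28-day post-treatment follow-up to the by-cycle AE tables, as Protocol 9.7 states.
2. Close the last cycle on the date SAP 9.1 already uses for treatment duration: last dose + 7 days if all 21 doses were given, otherwise the last dose date. Put later TEAEs, up to last dose + 28 days, in the follow-up column. AE and exposure tables for a cycle would then cover the same days.
3. State the denominator of each column.
4. As a wording correction only, use the last dose date as the single anchor in A2 Section 3 and stop equating it with the disposition-page date.

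Closing every last cycle at its Day 28 would be simpler but is not enough. If dosing stopped on Day 1, 27 off-drug days would stay in the cycle, and the follow-up column would cover only 1 to 21 days, depending on the day of the last dose. A cut at the start of new anticancer therapy should not be added, since neither document uses one in its AE rules.

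In the table's case of a last dose on Day 21, with all 21 doses given, the last cycle ends on Day 28 and the cycle percentage returns to p. The cost is SAP text and one derived period variable; no new data are needed and overall TEAE counts do not change. One minor downside is that last-cycle and follow-up windows will differ in length between subjects (follow-up is 21 days after a completed last cycle, 28 otherwise), which a table footnote should say.
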